## **Exploratory Endpoints and Relevant Variables**

*Change from Baseline to end of study period in Disease Activity Score (DAS28) and RAPID3 score*

- Baseline DAS (continuous, 0 to 10)
- Last DAS on study (continuous, 0 to 10) on study
- Baseline RAPID3 score (continuous)
- Last RAPID3 score (continuous) on study

Note: DAS28 ranges from 2 to 10, and is calculated as  $DAS28 = (0.56 * \sqrt{\text{Tender Joint Count}}) + 0.28 * \sqrt{\text{Swollen Joint Count}} + 0.7 * \ln(\text{ESR}) + 0.014 * (\text{Global Health})$ . The screening or rescreening ESR will be used for the calculation. Cumulative and weighted RAPID3 scores will be used.

*Change from Baseline to end of study period in Erythrocyte Sedimentation Rate (ESR)*

- Baseline ESR
- Last ESR on study

*Change from Baseline to end of study period in C-Reactive Protein (CRP)*

- Baseline CRP
- Last CRP on study

*Candidate biomarker expression in the peripheral blood of patients with RA-ILD over the 52 weeks of treatment and the study follow-up period*

- The exploratory analysis of candidate biomarkers will be a substudy performed at a later date.

*Changes from Baseline to end of study period in HRCT parameters evaluated by quantitative functional imaging*

- The quantitative parameters will be defined after the end of the trial, as exploratory analyses, and will include the following. These scores are separate from the radiologist -derived scores; they are computer interpretation of the scans, and range from 0 to 100.
  - DTA fibrosis score (total fibrosis score, dta\_fibrosis)
  - Honeycombing score (hc\_score)
  - Reticulation (reticular abnormality, ra\_score)
  - Ground glass abnormality score (ggo\_score)
- The data values that will be used:
  - Baseline HRCT quantitative measures
  - Last HRCT quantitative measures on study

*Changes from Baseline to Week 13, 26, 39 and final visit in the SGRQ*

- All measurements of SGRQ while on study, total score

- The SGRQ has 2 parts and 3 components (symptoms, activity and impacts). Scores for each component range from 0 to 100 with higher scores meaning more disability. A total score is calculated from component scores with a range from 0 to 100 with higher scores meaning more disability.

*Changes from Baseline to Week 13, 26, 39 and final visit in Dyspnea 12 questionnaire*

- All measurements of Dyspnea 12 while on study, total score
- The Dyspnea 12 has 12 questions scored 0 (none) to 3 (severe). Score are added up for total (0 to 36) with higher scores indicating greater severity of symptoms.

*Changes from Baseline to Week 13, 26, 39 and final visit in LCQ*

- All measurements of LCQ while on study, total score
- The scores are calculated as a mean for each domain and total score is found by adding the domain scores.

*Changes from Baseline to Week 13, 26, 39 and final visit in the Patient Global Assessment*

- All measurements of Patient Global Assessment while on study, total score
- The Patient Global Assessment has 3 questions that are compared separately for change. One question is scaled 0 to 10 and two questions are scaled on a likert scale.

*Changes from Baseline to Week 13, 26, 39 and final visit in the Health Assessment Questionnaire*

- All measurements of Stanford Health Assessment Questionnaire while on study and date.  
The Health Assessment Questionnaire has 8 sections scored 0 – 3. Using the highest score in each section, the Health Assessment Questionnaire Score is the average across all sections with data (see Fries, et al., 1980)

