### **7.1.1 Laboratory Assessments**

#### Routine Clinical Laboratory Tests

The following research related assessments will be performed locally at each clinical site, according to Appendix A, as summarized below:

- Hematology (complete blood count with platelet count and automated differential)
- Serum chemistry profile (albumin, alkaline phosphatase, ALT/SGPT, AST/SGOT, total bilirubin, calcium, creatinine, glomerular filtration rate (eGFR), gamma-glutamyl transferase [GGT], glucose, potassium, sodium, BUN, uric acid and amylase)
- Blood Pregnancy test for women of childbearing capacity
- Serology assessments include Erythrocyte Sedimentation Rate (ESR), Rheumatoid Factor (RF), C-Reactive Protein (CRP), and Cyclic Citrullinated Peptide (CCP)

It is the investigator's responsibility to perform clinical laboratory assessments more frequently, if clinically indicated.

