**Week 52 (Visit 11) ( $\pm$  4 weeks)**

At the Week 52 Visit, the following procedures will be performed:

1. Review of AEs/SAEs, concomitant medications, oxygen use
2. Physical examination, resting oxygen saturation, vital signs, and weight
3. Clinical laboratory assessments, including hematology, serum chemistries, serologic tests, and blood pregnancy test for women of childbearing capacity
4. Biomarkers (See Appendix A)
5. Blood samples for genetic research (DNA PAXgene samples) - Optional
6. Spirometry (FVC, FEV1 without bronchodilator administration)
7. Lung volumes, DLCO or TLCO
8. Patient Reported Outcome Questionnaires (See Appendix A)
9. Study Medication Accountability, including collection of any unused study treatment
10. Study Medication Dosing review (participant diary)
11. HRCT scan

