## **Exploratory Endpoints**

The following exploratory outcomes will be analyzed using the ITT population:

1. Change from Baseline to end of study in Disease Activity Score (DAS)
2. Change from baseline to end of study in Routine Assessment of Patient Index Data 3 (RAPID3) score
3. Change from Baseline to end of study in Erythrocyte Sedimentation Rate (ESR)
4. Change from Baseline to end of study in C-Reactive Protein (CRP)
5. Candidate biomarker expression in the peripheral blood of patients with RA-ILD over the 52 weeks of treatment.
6. Changes from Baseline to end of study in high resolution computed tomography (HRCT) parameters evaluated by quantitative functional imaging
7. Changes from Baseline to Week 13, 26, 39 and final visit in the St. George's Respiratory Questionnaire (SGRQ)
8. Changes from Baseline to Week 13, 26, 39 and final visit in Dyspnea 12 questionnaire
9. Changes from Baseline to Week 13, 26, 39 and final visit in Leicester Cough Questionnaire (LCQ)
10. Changes from Baseline to Week 13, 26, 39 and final visit in the Patient global assessment
11. Changes from Baseline to Week 13, 26, 39 and final visit in the Health assessment questionnaire

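### The SAP does not confine its screening-ESR rule to the baseline DAS28; read literally, ESR cancels out of the exploratory change-in-DAS28 endpoint

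*SAP*

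**What the plan says.** The first exploratory endpoint in the SAP is "Change from Baseline to end of study in Disease Activity Score (DAS"). Under Exploratory Endpoints and Relevant Variables, the SAP builds it from a baseline DAS and a second input, "Last DAS on study (continuous, 0 to 10) on study". A note then gives a single DAS28 formula with four terms: tender joint count, swollen joint count, ln(ESR) with coefficient 0.7, and global health. The note adds: "The screening or rescreening ESR will be used for the calculation". It does not say which of the two scores this covers.

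An end-of-study ESR is planned. Protocol 7.1.1 states "Serology assessments include Erythrocyte Sedimentation Rate (ESR), Rheumatoid Factor (RF"), followed by further tests. The Week 52 list in Protocol 7.2.2 contains "Clinical laboratory assessments, including hematology, serum chemistries, serologic tests, and blood pregnancy test for women of childbearing capacity", and the Early Termination list has the same item. Both visits also collect joint counts and the patient global score. The SAP itself relies on a post-baseline value, "Last ESR on study", for the separate ESR-change endpoint.

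**The concern.** A programmer working from the SAP has one formula, two scores to compute and one instruction on ESR. If the instruction is applied to both scores, the last DAS28 combines joint counts and global health from about Week 52 with an ESR drawn before treatment. The ESR component then cannot contribute to the change, although the result would still be labelled change in DAS28.

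A second programmer could reasonably apply the instruction to the baseline score only and use the Week 52 ESR for the last score. The two would report different values for the same pre-specified endpoint. Protocol 2.1.2 describes pirfenidone's action as thought to be partly anti-inflammatory, so an inflammatory marker is a relevant part of the score to keep.

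**Working it through.** The plan attaches no sample size, power or expected effect to this endpoint, so there is no stated figure to reproduce. The check is algebra on the SAP's own formula.

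**Inputs.** From the SAP note, with TJC and SJC the tender and swollen joint counts and GH global health:

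DAS28 = 0.56 × √TJC + 0.28 × √SJC + 0.7 × ln(ESR) + 0.014 × GH

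From Protocol 10.4.2: a change outcome is the last value less the baseline value.

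**ESR part of the change.**

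- Screening ESR in both scores: 0.7 × ln(ESR_screen) − 0.7 × ln(ESR_screen) = 0 for every participant, whatever the end-of-study ESR.
- End-of-study ESR in the last score: 0.7 × ln(ESR_end) − 0.7 × ln(ESR_screen) = 0.7 × ln(ESR_end / ESR_screen).

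The second expression is what the literal reading omits. The ratios below are assumptions chosen to show the scale:

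| Assumed ESR_end / ESR_screen | Omitted DAS28 units |
|---|---|
| 0.25 | −0.970 |
| 0.5 | −0.485 |
| 0.75 | −0.201 |
| 1 | 0 |
| 1.5 | +0.284 |
| 2 | +0.485 |

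**Worked case for one participant (all values assumed).** TJC goes from 6 to 3, SJC from 4 to 2, GH from 50 to 30 and ESR from 40 to 20.

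- Baseline: 1.372 + 0.560 + 2.582 + 0.700 = 5.214.
- Last score with its own ESR: 0.970 + 0.396 + 2.097 + 0.420 = 3.883. Change = −1.331.
- Last score with the screening ESR: 0.970 + 0.396 + 2.582 + 0.420 = 4.368. Change = −0.846.
- Difference: −1.331 − (−0.846) = −0.485 = 0.7 × ln(0.5), as the table gives.

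**What this means for the comparison of arms.** These are amounts per participant. In a comparison of mean change, the omitted amount is 0.7 × (mean ln ratio on pirfenidone − mean ln ratio on placebo). It is zero if ESR moves equally in both arms. The documents give no expected ESR change in either arm, so the loss in the treatment contrast cannot be sized.

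**The case against.** The strongest reply is that the sentence concerns the baseline score only. Several things support this:

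- The Visit 2 procedure list in Protocol 7.2.1 includes joint counts and patient global but no ESR, while screening includes serology. Someone computing a baseline DAS28 therefore needs to be told which ESR to pair with those joint counts.
- The SAP's Definition of Baseline uses the same pairing of screening and rescreening values as its fallback for patient-reported outcomes, so this is the SAP's vocabulary for baseline.
- The Protocol's paragraph on DAS28 in 7.1.2 scores it from examination, laboratory results and patient global, and does not say to reuse an earlier laboratory value.
- The SAP uses the last on-study ESR for another endpoint a few lines later, so its authors knew that the value would exist.

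This reading is plausible and probably the intended one. It does not remove the problem, because the sentence follows a formula that serves both scores and no text in the protocol or SAP restricts it. The SAP's general baseline rule already sends ESR to screening if it is not collected at randomization, so a reader may take the extra sentence as saying something more. The SAP also cites a separate variable file, which is not among the documents, but it cites that file by its primary and secondary outcomes tab, and DAS28 is exploratory.

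Two stronger readings are tempting, and the documents do not support them. A reader might infer that the endpoint stops measuring change in disease activity. It does not: three of the four terms still move, swollen joint count also reflects inflammation, and ESR and CRP changes are exploratory endpoints in their own right. A reader might also take it as settled that no ESR is drawn at Visit 2. The Visit 2 list suggests so, but the serology row of Appendix A appears to carry a mark at that visit, and the table is too broken in the available text to decide.

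**Conclusion.** The concern holds as a wording gap with a conditional consequence. If the sentence is followed as written, the ESR contribution to the change in DAS28 is exactly zero for every participant, and the omitted part is 0.7 × ln(ESR_end / ESR_screen). The cancellation follows from the SAP's formula with no further assumption. The 0.49 and 0.28 unit figures rest on assumed ESR ratios and say nothing about what this trial will observe.

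The practical weight is low. This is one of eleven exploratory endpoints, Protocol 10.4.2 has such analyses reported as exploratory, and no primary or secondary endpoint uses DAS28. The documents do not show a deliberate decision to hold ESR fixed, and that should not be inferred.

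**What to change.** Replace the sentence in the SAP's DAS28 note with two clauses: the baseline DAS28 uses the screening or rescreening ESR; the last DAS28 uses the ESR from the same end-of-study visit as its joint counts (Week 52 or Early Termination), not the screening ESR. The new text needs no statement about whether ESR is drawn at Visit 2.

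A rule for a missing end-of-study ESR is optional. It may be useful because Protocol 17.3 lets visits go remote and does not list serology among the assessments expected at them.

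The cost is one SAP sentence, made before database lock. It needs no new data collection and changes no other endpoint.

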## **Planned Sample Size**

The planned sample size for this trial was 270 participants randomized with equal probability to one of two treatment arms. The considerations delineated in the protocol show that 254 participants with complete data provide at least 85% power to demonstrate the treatment arm difference in terms of the combined primary endpoint reached by week 52, defined as either death or a decline from baseline of  $\geq 10$  percentage points in the percent predicted FVC. The robustness of this determination under a variety of feasible scenarios is also demonstrated in the protocol. The planned number of participants randomized was 270 because of possible loss of data due to participants dropping out before week 52 or other reasons.

## **Actual Sample Size**

Enrolment at centers was interrupted by the COVID-19 pandemic during March, 2020. After all centers were shut down for approximately three months, and after an interim DSMB meeting that focussed on the interruption of recruitment, a decision was made to permanently close enrolment. The final sample size is 123 randomized participants. The last participant was randomized on March 24, 2020.

## **General Analysis Considerations**

### **Timing of Analyses**

Data cleaning will be performed throughout the enrolment period, and will continue and through the 12-month study period of the last participant randomized. Data cleaning will be conducted in conjunction with a blind data review while the study is ongoing. The database will be locked and the final analysis will be performed after the last participant completes visit 12 at the end of the follow-up period, and after all outstanding data queries and discrepancies are resolved. This statistical analysis plan will be finalized before closure of the database and before any final analyses are conducted. Independent study monitoring will be conducted by SABER in adherence to the Good Clinical Practice guidelines.

## **Analysis Populations**

Each participant's inclusion or exclusion status with regard to each analysis population will be determined prior to breaking the blind. For relevant variables, please refer to the accompanying file (TRAIL1 endpoints and dataset variable names.xlsx, Analysis Population type tab.)

### **Intention to Treat (ITT) population (full analysis set):**

Defined as all participants who were randomized. The ITT population will be used for all primary, secondary, and exploratory efficacy analyses.

### **Safety population (as-treated population)**

Defined as all randomized participants who received any study medication and who received at least one study medication dose. The Safety population will be used for safety-related analyses.

### **Per Protocol population**

Defined as all randomized participants who did not deviate from the protocol, who satisfy all eligibility criteria, and who are compliant with study medication, determined on a per-participant basis by trial leadership before database lock. The Per Protocol population will be used for sensitivity analyses to demonstrate robustness of the results, and for selected sub-studies to be determined. Out of visit window visits do not automatically disqualify participants from the per protocol population. If a visit is less than four weeks out of the window (either before or after,) then it is included in the Per Protocol population. Prohibited medications will exclude participants from the Per Protocol population. Medication compliance is required for inclusion in the Per Protocol population, and is defined elsewhere in this document as having taken at least 80% and not more than 120% of dispensed pills according to pill diaries. Other protocol deviations will be discussed on a case-by-case basis prior to the final database lock and while all team members are blinded to treatment assignments.

## **Sensitivity Analyses**

To assess the robustness of the primary analysis of the primary endpoint, the following two sensitivity analyses will be performed. (1) The analysis of the primary composite endpoint will be repeated using the Per-Protocol population. (2) The analysis of the primary composite endpoint will be repeated using an adaptation of the Per-Protocol population where the lower threshold for medication compliance will be reduced from 80% to 65%.

## **Coronavirus Disease 19 (COVID-19)**

The effect of COVID-19 on TRAIL1 will be investigated as follows: Protocol deviations due to COVID-19 will be presented and visits out of window due to COVID-19 will also be identified. Sensitivity analyses will be determined if necessary prior to database lock, and may include the following: Excluding all affected participants, using time-varying covariates to identify measurements taken during the affected period, increasing the duration of visit windows beyond those specified in the protocol, setting all data in a participant's affected period to missing and imputing values. (reference: Ongoing trials during COVID-19: Quantitative strategies and methodological aspects: Cytel, Inc. 2020.)

### **COVID-19-related factors that have the potential to impact this trial:**

- COVID-19 infection resulting in voluntary or mandatory dropout
- Different investigator(s) filling in
- Study center closures resulting in loss to follow-up
- Stopped enrollment resulting in study termination or delay
- Delayed assessments and expanded protocol visit windows
- Missed visits and/or assessments leading to partial data collection
- Alternative data collection, phone visits, exchangeability of methods, validation
- Stopping drug due to safety concerns
- Stopping drug due to lack of lab monitoring

- Concomitant meds due to COVID-19, and interaction with the Investigational Medicinal Product (IMP)

## **Covariates and Subgroups**

### **Covariates**

Pre-specified baseline covariates known to be related to specific endpoints will be included as predictors in the primary analyses. One covariate has been pre-specified: the HRCT pattern, categorized as usual interstitial pneumonia (UIP)-like fibrotic pattern versus other fibrotic patterns.

### **Subgroups**

Subgroup analyses are considered exploratory. Subgroupings were selected for pre-specification where there is an expectation of differential treatment effects. The p-value for the interaction between the subgroup variable and treatment arm will be reported. Sufficient power to reject a null hypothesis for the interaction is not anticipated. If the interaction (difference in the treatment effects among the subgroups) is judged to be clinically important, then subgroup-specific estimates of the treatment effect and 95% confidence intervals will be reported. Pre-specified subgroups will include sex, race (white, black or African American, Asian, native Hawaiian or other pacific islander, American Indian or Alaska native,) and ethnicity (Hispanic or Latino.)

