### **Multiple Testing**

As this is a Phase II trial with only one single pre-specified primary endpoint, adjustment for multiple testing in the analyses is not planned for the primary endpoint or for the hypothesis-generating

secondary endpoints. In the exploration of the pre-specified subgroups, estimates of effect and 95% confidence intervals will be reported with an accompanying statement regarding multiplicity and the exploratory nature of the subgroup analyses.

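### The SAP shows subgroup estimates only if the observed interaction is judged important, with no criterion, while its Multiple Testing section promises them without condition

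*SAP*

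**What the plan says.** The SAP's Subgroups section pre-specifies three factors: sex, race (five listed categories) and ethnicity. It says that "Subgroup analyses are considered exploratory" and that "Sufficient power to reject a null hypothesis for the interaction is not anticipated".

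It then sets two reporting rules. The first has no condition: "The p-value for the interaction between the subgroup variable and treatment arm will be reported". The second has one. It opens with "If the interaction (difference in the treatment effects among the subgroups" and, if that difference "is judged to be clinically important, then subgroup-specific estimates of the treatment effect and 95% confidence intervals will be reported". The section gives no threshold or effect scale for the judgement, does not say who makes it or when, and does not require that person to be blinded. It also does not say which endpoint the subgroup analyses concern.

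The SAP's Multiple Testing section covers the same factors: "In the exploration of the pre-specified subgroups, estimates of effect and 95% confidence intervals will be reported with an accompanying statement regarding multiplicity". It adds that the statement will note their exploratory nature. It sets no condition on reporting, and no other section reconciles the two.

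**The concern.** There are two problems.

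- **Wording.** When an interaction is judged unimportant, the Subgroups section asks for a p-value only, while the Multiple Testing section, read as written, asks for estimates and intervals too. Whoever programs the tables cannot tell which rule to follow.
- **Selection.** The condition is applied to the observed difference in treatment effects, so whether an estimate appears depends on its own value. If noise can easily produce large apparent interactions, the estimates that appear will tend to overstate heterogeneity. For the remaining factors the reader gets a p-value without direction, size or precision, and cannot tell a consistent effect from an imprecise one.

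The SAP protects comparable discretionary decisions. Membership of the analysis populations is fixed before the blind is broken, case-by-case deviations are settled by a blinded team, and any COVID-19 sensitivity analyses are chosen before database lock. The subgroup judgement has no such protection.

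**Working it through.** **Comparing the two rules**

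| Output | SAP, Subgroups | SAP, Multiple Testing |
|---|---|---|
| Interaction p-value | always | not mentioned |
| Subgroup estimates and 95% CIs | only if the interaction is judged important | reported, no condition stated |
| Criterion for importance | none | not applicable |

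**Reproducing the plan's own figure**

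The documents give no calculation for subgroups, so I first checked the planning rates against the stated sample size. Protocol section 10.2.1 gives 0.32 on placebo, 0.16 on pirfenidone, two-sided alpha 0.05, 85% power and 127 per arm.

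n = [1.960 × √(2 × 0.24 × 0.76) + 1.036 × √(0.32 × 0.68 + 0.16 × 0.84)]² / 0.16² = (1.184 + 0.615)² / 0.0256 ≈ 126.4, which rounds up to 127. Power at 127 per arm is 0.852. The plan's figure is reproduced.

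**Noise in an observed interaction at the actual size**

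Inputs from the documents:
- 123 randomized (SAP, Actual Sample Size)
- 1:1 allocation (protocol section 4.1), so 61.5 per arm
- rates 0.32 and 0.16, giving about 61.5 × 0.48 = 29.5 expected events

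My assumptions, because the documents give none of these:
- the primary endpoint is the one analysed
- the factor has two levels, with a share f of participants in one level, from 50:50 to 90:10
- the same event rates apply in both levels, so there is no true interaction
- importance is judged by whether the observed ratio of odds ratios (ROR) reaches 1.5-, 2- or 3-fold in either direction

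The variance of the log ROR is the sum over the four cells of 1/(np) + 1/(n(1−p)), which simplifies to

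Var = (1/61.5) × (1/0.2176 + 1/0.1344) / [f(1−f)] = 0.1957 / [f(1−f)].

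- At 50:50: SE = √(0.1957/0.25) = 0.885.
- At 90:10: SE = √(0.1957/0.09) = 1.475.

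The chance of passing a cut-off t is 2 × [1 − Φ(ln t / SE)]. At 50:50 and t = 2 this is 2 × [1 − Φ(0.693/0.885)] = 0.433.

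| Split | SE | 1.5-fold | 2-fold | 3-fold |
|---|---|---|---|---|
| 50:50 | 0.885 | 0.647 | 0.433 | 0.214 |
| 60:40 | 0.903 | 0.653 | 0.443 | 0.224 |
| 70:30 | 0.965 | 0.674 | 0.473 | 0.255 |
| 80:20 | 1.106 | 0.714 | 0.531 | 0.321 |
| 90:10 | 1.475 | 0.783 | 0.638 | 0.456 |

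A simulation with whole-number cells (62 per arm, 0.5 added to each count) gave 0.637 to 0.753, 0.425 to 0.590 and 0.211 to 0.386 for the three cut-offs. Among simulated results passing 2-fold, the median apparent ROR was 2.99 to 3.76, although the true value is 1.

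Power to detect a true 2-fold ROR at the 5% level is 12.3% at 50:50 and 7.6% at 90:10. The ROR detectable with 80% power at 50:50 is exp[(1.960 + 0.842) × 0.885] ≈ 11.9. This agrees with the SAP's own remark that interaction power is not expected to be sufficient.

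**The case against.** The SAP already contains real safeguards. The factors are named in advance, the analyses are labelled exploratory, low interaction power is admitted, and reporting does not hinge on p < 0.05. The interaction p-value appears for every factor. A reader might infer that the plan conceals null subgroups or shows only the ones that look different. The documents do not support that: every tested factor and its p-value will be visible, and only the estimates and intervals are filtered.

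A reader might also call the two sections flatly contradictory. The Multiple Testing sentence can be read more narrowly, as saying that whatever estimates the Subgroups section releases will carry a caveat. Its wording states no such limit, so the misalignment stands, but it is an ambiguity to be resolved and not proof of two irreconcilable instructions.

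The arithmetic has limits as well. Judgement need not be a mechanical cut on a point estimate; it could weigh precision and the p-value. The percentages are therefore not the chance that this SAP would report a subgroup. It is also tempting to compound the per-factor figure across three factors. That would treat all three as independent binary factors, but race has five listed levels and no single ROR, and the documents give no subgroup splits and no basis for independence. I give no combined figure.

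What stands is that the size of an observed interaction at this sample size is a poor guide to whether it is real, and that the plan sets no criterion for judging it.

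**Conclusion.** The point holds in a limited form. The two sections need to be aligned, and the conditional rule selects estimates by result, without a criterion or a requirement for blinding. The estimates shown would tend to exaggerate heterogeneity.

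The per-factor chance of passing by noise alone is about 65-78% at 1.5-fold, 43-64% at 2-fold and 21-46% at 3-fold. These figures rest on the planning event rates holding in both levels and on the assumed two-level splits and cut-offs. They illustrate how noisy the trigger is and do not predict what would be reported. The issue is minor: it concerns exploratory output and leaves the primary analysis untouched.

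**What to change.** - Delete the condition in the SAP's Subgroups section and follow the Multiple Testing section.
- Report the treatment estimate, 95% CI and interaction p-value for every pre-specified subgroup in one table or forest plot, with the multiplicity and exploratory statement already planned.
- Before unblinding, state that race or ethnicity levels too sparse to estimate will be pooled or shown as counts only. Without this, an unconditional rule could call for odds ratios that cannot be computed among 123 participants; the SAP already foresees sparse-data fitting problems in its Multi-center Studies and Efficacy Analyses sections.

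The cost is one deleted sentence, one short rule on sparse levels and one extra table, some of whose intervals will be wide. No new data are needed.
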